## Statistical Analysis Plan

Sponsor: Zogenix International Limited; Protocol No.: ZX008 Study 2 (ZX008-1501 and ZX008-1502)

---

$I_0 = \text{Date}_1 - \text{Date}_0$ ,

and the time from the last seizure to end of treatment as

$I_5 = \text{LDT} - \text{Date}_5$ .

Here the duration of the longest interval = Maximum ( $I_0, I_1, I_2, I_3, I_4, I_5$ ).

If the subject does not experience a seizure during treatment, then the last available diary date will be used to compute the duration of the longest interval as follows:

The longest interval = last available diary date – Date0

The median time of the longest convulsive seizure-free interval will be presented. Additional summary statistics will be presented, including mean, minimum, maximum, the 25th and 75th percentiles, 95% confidence intervals on the difference in medians between groups (Hodges-Lehman estimator).

The Wilcoxon rank sum test will be used to test for differences between each treatment arm and placebo, and the p-value from this test will be presented. A histogram presenting the percentage of subjects whose longest seizure free interval is <10, 11-20, 21-40, 41-60, 61-84, and ≥84 days will accompany all descriptive statistics and all data will be provided in a data listing.

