### **3.4 RANDOMIZATION**

Treatment assignments are assigned independently within Study 1501 and Study 1502. Specifically, each trial assigns treatments using randomized permuted blocks; i.e., treatments are assigned in blocks to ensure exact balance among treatments within each block. The blocking is applied across the entire trial such that newly enrolled subjects are randomized to the next available treatment regardless of the site or country where they enroll. This approach assures balance among treatment groups within each trial at any point during enrollment. Combining data from two trials means that two sets of randomized blocks will be used, which would have approximately the same effect as doubling the block size in a single trial. Increasing the block size is expected to have little impact on a trial of 120 subjects. Moreover, combining the first 120 randomized subjects from Study 1501 and Study 1502 to create Study 1 preserves balance among the three treatment groups in each of Study 1 and Study 2, yielding approximately 40 subjects per arm, the number required to maintain full statistical power.

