## **6. STATISTICAL METHODOLOGY**

### **6.1 STATISTICAL AND ANALYTICAL ISSUES**

#### **6.1.1 Statistical Methods**

Tabulations for Study 1 will be produced for appropriate demographic, baseline, efficacy and safety parameters. Continuous data will be summarized using descriptive statistics including the number of observations, means, standard deviations, medians, lower and upper quartiles, and ranges. Categorical variables will be summarized with frequencies and percentages.

Confidence intervals will be calculated for key parameters or estimates as described in the sections below.

All efficacy parameters will be summarized by descriptive statistics. Two-sided statistical significance testing (alpha level = 0.05) comparing each active treatment to placebo will be performed for the primary and secondary endpoints as described below, unless otherwise noted.

All descriptive statistical analyses will be performed using SAS statistical software (Version 9.3, unless otherwise noted). Adverse events will be coded using the most recent MedDRA version available at the time of analysis. Concomitant medications will be coded using the most recent version of World Health Organization (WHO) Drug.

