### 6.1.2 Multiplicity Strategy and Testing Hierarchy

Multiplicity issues in the statistical inference in this study arise from two sources: (a) multiple treatment comparisons, and (b) multiple endpoints.

The efficacy analyses will employ a serial gatekeeper strategy to maintain the Type 1 error rate at  $\alpha=0.05$  across the family of analyses that support the primary and key secondary objectives.

All statistical analyses will be performed and results tabulated with test statistics, p-values, and/or 95% confidence intervals.

Formal statistical testing will be performed for 1 primary endpoint and 2 secondary endpoints, for the comparison of ZX008 0.8 mg/kg with Placebo, and between ZX008 0.2 mg/kg with Placebo. Hence there are 6 formal hypothesis tests: 1 primary hypothesis test and 5 secondary hypothesis tests. To preserve the overall Type 1 error rate at  $\alpha=0.05$ , these tests will proceed as follows:

Step 1: The primary efficacy endpoint (mean convulsive seizure frequency per 28 days) will be formally tested first between the 0.8 mg/kg and Placebo group. If the comparison is statistically significant at the  $\alpha=0.05$  (2-sided) level, hypothesis testing will proceed to Step 2. Otherwise formal testing of the other hypotheses stops.

Step 2: The secondary efficacy endpoint, the proportion of subjects who achieve a  $\geq 50\%$  reduction from baseline in convulsive seizure frequency, will be compared between the 0.8 mg/kg and Placebo group. If the comparison is statistically significant at the  $\alpha=0.05$  (2-sided) level, hypothesis testing will proceed to Step 3. Otherwise formal testing of the other hypotheses stops.

Step 3: The endpoint, the longest convulsive seizure-free interval will be compared between 0.8 mg/kg and Placebo. If the comparison is statistically significant at the  $\alpha=0.05$  (2-sided) level, hypothesis testing will proceed to Step 4. Otherwise formal testing stops.

Step 4: The mean convulsive seizure frequency per 28 days will be formally tested first between the 0.2 mg/kg and Placebo group. If the comparison is statistically significant at the  $\alpha=0.05$  (2-sided) level, hypothesis testing will proceed to Step 5. Otherwise formal testing of the other hypotheses stops.

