### **6.3.3.5 Incidence of Rescue Medication Usage**

Use of rescue medication is recorded on the daily diary. In the event of prolonged seizures or status epilepticus, rescue medication is administered according to each subject's personalized regimen consisting of one or more medications. If the first rescue administration does not control the seizures, a second or even third round might be administered. They second and third round might use different medications or different doses than the first round of rescue meds.

Rescue medication will be summarized by treatment group and by active treatment vs. Placebo for the following:

- The number of days rescue medication was taken (normalized to 28 days) will be summarized separately for the Baseline and T+M periods by the mean (SD) as well as the median and range. Multiple medications taken on the same day will be counted once for that day. The ZX008 group will be compared to the placebo group using a rank ANCOVA analogous to that described in [Section 6.3.1.1](#). Specifically, the rank ANCOVA will use the ranks of rescue medication frequency during T+M as the response, and will incorporate treatment group as a factor and the ranks of rescue medication frequency during Baseline as a covariate.

- The number of medications used per episode will be summarized using similar descriptive statistics as above. Rescue medications related to an episode of SE are considered to be all rescue administered on the day of the SE (or seizure lasting >10 min). If more than one episode of SE or a seizure lasting >10 min occurred in a single day, the rescue medication for that episode is all rescue administered after the seizure until the start time of the next prolonged seizure.

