### 2.5. Determination of Sample Size

The sample sizes for Zogenix Studies 1501 and 1502 were calculated based on the results of two trials with stiripentol reported in the European Public Assessment Report (EPAR) for stiripentol (EMA, 2007). The stiripentol EPAR summarizes the results from two studies: STICLO France and STICLO Italy. In the stiripentol groups, the standard deviation (SD) of the percentage change in seizure frequency from baseline to month 2 was 42% in the French trial and 26% in the Italian trial. The analogous SDs for placebo groups were 38% and 62%. An SD of 50% was assumed for the primary analysis in Protocols 1501 and 1502 that compares ZX008 0.8 mg/kg/day to placebo on the change from baseline in seizure frequency. Using a two-sided test at the  $\alpha=0.05$  significance level, a sample size of 35 subjects per treatment group affords 90% power to detect a difference in mean change from baseline of 40 percentage points. Similar assumptions and calculations yielded a requirement for an additional 35 subjects in the 0.2 mg/kg/day ZX008 group. The total sample size for each study was therefore set at 105 subjects.

In December 2016 results from a double-blind, placebo-controlled Phase 3 study with Epidiolex® (cannabidiol) to treat seizures in Dravet syndrome were presented at the American Epilepsy Society Meeting (<http://ir.gwpharm.com/events.cfm>). In the Epidiolex study, active drug reduced seizures by 39% compared to a reduction of 13% in the placebo. Review of the data suggested that the standard deviation was relatively large, likely above 50% in both treatment groups. In consideration of this new data, the sample size was re-estimated for the ZX008 studies to assume a SD of 55%, higher than the previous estimate of 50%. Other assumptions in the sample size calculation remained unchanged. A sample size of approximately 120 subjects (40 per arm) affords 90% power to detect a difference in mean change from baseline of 40 percentage points with 55% SD. Considering the variability seen in the STILCO and Epidiolex trials, the sample size for Study 1 and Study 2 is set at 120 subjects, 40 per treatment arm. Note that the change in assumed SD was based entirely on data from external trials. Efficacy data from both Study 1501 and 1502 are still blinded and were not used in re-estimating the required sample size.

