Step 5: The secondary efficacy endpoint, the proportion of subjects who achieve a  $\geq 50\%$  reduction from baseline in convulsive seizure frequency, will be compared between the 0.2 mg/kg and Placebo group. If the comparison is statistically significant at the  $\alpha=0.05$  (2-sided) level, hypothesis testing will proceed to Step 6. Otherwise formal testing of the other hypotheses stops.

Step 6: The endpoint, the longest convulsive seizure-free interval will be compared between 0.2 mg/kg and Placebo using a significance level of  $\alpha=0.05$  (2-sided).

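### The longest seizure-free interval test at Steps 3 and 6 is valid but not adjusted for baseline seizure frequency, and may give up material power

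*SAP*

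**What the plan says.** For the longest interval, Study 2 SAP section 8.2.1 and Study 1 SAP section 6.3.2.3 use the same words: "The Wilcoxon rank sum test will be used to test for differences between each treatment arm and placebo". Neither section names a covariate or a stratum. The estimate reported with the test is a Hodges-Lehmann interval for the difference in medians.

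The endpoint appears twice in the serial gate, which is the same in both plans:
- "Step 3: The endpoint, the longest convulsive seizure-free interval will be compared between 0.8 mg/kg and Placebo". If this fails, formal testing stops, and Steps 4 to 6 are all of the 0.2 mg/kg/day hypotheses.
- "Step 6: The endpoint, the longest convulsive seizure-free interval will be compared between 0.2 mg/kg and Placebo". This is the last step.

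Every step is tested at the two-sided 0.05 level.

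Other endpoints are handled differently. In the Study 2 SAP:
- The primary ANCOVA (section 8.1) adjusts for log baseline CSF and age group. Its nonparametric fallback uses ranked baseline CSF.
- Seizure-free days, non-convulsive seizures and rescue days (section 8.2.2) all take the baseline value as covariate. For rescue days: "Specifically, the rank ANCOVA will use the ranks of rescue medication frequency during T+M as the response", with ranked baseline frequency as covariate.

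The sections on changes from the protocol (Study 1 SAP 6.9, Study 2 SAP 12) explain why the log-rank test was dropped for this endpoint. The reasons concern censoring and say nothing about baseline or age.

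**The concern.** How long a child goes without a convulsive seizure depends heavily on how often that child seizes, and 42 days of baseline diary measure that rate directly. A two-sample rank test leaves this between-child variation in the error term. As a result, a gated key secondary endpoint gets a less efficient analysis than several endpoints outside the gate.

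At Step 3, a miss caused by avoidable noise would close formal testing of the lower dose, whatever that dose's effect.

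**Working it through.** **The plan's own figure.** The only power statement (Study 2 SAP section 2.5) is for the primary endpoint. It says that the planned size, 40 in each of three arms, "affords 90% power to detect a difference in mean change from baseline of 40 percentage points with 55% SD".
- n per arm = 2(1.960 + 1.282)² × 55²/40² = 39.7, rounded up to 40.
- Power at 40 per arm = Φ(40/(55√(2/40)) − 1.960) = Φ(1.29) = 0.902. A t-test calculation gives 0.895.

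The figure reproduces. It does not cover the longest interval, for which neither plan states a power, effect size, SD or baseline correlation.

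**Gain from adjustment as a function of rho.** Adjusting the ranks for ranked baseline CSF multiplies the residual variance by about 1 − rho². If unadjusted power is p0, then

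adjusted power = Φ((1.960 + z(p0))/√(1 − rho²) − 1.960).

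Example: p0 = 0.80 and rho = 0.5 give (1.960 + 0.842)/0.866 − 1.960 = 1.275, so power is 89.9%.

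| rho | from 60% | from 80% | n per arm matching 40 unadjusted, 40(1 − rho²) |
|---|---|---|---|
| 0.2 | 61.8% | 81.6% | 38.4 |
| 0.3 | 64.1% | 83.6% | 36.4 |
| 0.5 | 72.4% | 89.9% | 30.0 |
| 0.6 | 79.0% | 93.8% | 25.6 |
| 0.7 | 87.3% | 97.5% | 20.4 |

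The gains are about 2-4 points at rho 0.2-0.3, 10-12 at 0.5 and 14-27 at 0.6-0.7.

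**Simulation of the endpoint.** From the plan: 40 per arm, 42 baseline days, 98 days of titration plus maintenance, 25% of subjects under 6 years, two-sided 5%. Assumed: median baseline 20 seizures per 28 days, between-subject log-SD 0.8 or 1.1, within-subject log-change SD 0.5, 0.8 or 1.2, seizures single or in bouts of three, no age effect. There were 600 runs per cell. The absolute rank correlation came out between about 0.45 and 0.84.

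| Rate ratio vs placebo | Smallest gap (Wilcoxon vs rank ANCOVA) | Largest gap |
|---|---|---|
| 0.6 | 30% vs 35% | 41% vs 91% |
| 0.5 | 52% vs 59% | 60% vs 95% |
| 0.4 | 97% vs 100% | 76% vs 98% |

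Under no effect, rejection averaged over the 12 cells was 5.3% for the Wilcoxon and 4.9% for the rank ANCOVA. Adding age alone changed power by about 1 point or less.

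**Effect on the gate.** Step 3 counts only if Steps 1 and 2 succeed. A second simulation gives the joint chance of reaching Step 4. It assumed a baseline log-SD of 1, a log-change SD of 0.7, gamma-mixed counts with shape 1, and 800 runs per cell.

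| Reduction | Step 3 alone, Wilcoxon vs rank ANCOVA | Reaching Step 4 |
|---|---|---|
| 50% | 66% vs 92% | 61% vs 82% |
| 40% | 41% vs 69% | 29% vs 49% |

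With a log-change SD of 1.0 and a 50% reduction, Step 3 alone is 55% vs 71% and reaching Step 4 is 42% vs 52%.

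**The case against.** The Wilcoxon test holds its type I error. It was chosen deliberately to replace a log-rank test with a censoring problem, and it pairs naturally with the Hodges-Lehmann interval. All of this stands: the choice is not an error. But the censoring argument does not bear on baseline adjustment, because a rank ANCOVA uses ranks of the same interval. A real cost of changing is that an adjusted p-value and an unadjusted estimate may occasionally differ.

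Four stronger readings go beyond the documents:
- *A large share of power is certainly lost.* That needs a high rho, which the plans do not report. A strong correlation is plausible, since the baseline bands in section 8.1 run from below 10 to above 50 per 28 days, but it remains an assumption. Where unadjusted power is about 95% or more, little is left to gain.
- *This is the least efficient test in the sequence.* With a log-change SD of 1.0, the Step 2 responder test and the Wilcoxon had similar simulated power: 61% vs 55% at a 50% reduction, 20% vs 20% at 30%.
- *Leaving out the age stratum drives the loss.* Baseline CSF carries nearly all of the gain in these scenarios, though they assumed no age effect.
- *Leaving out study is a serious omission.* It is true that "Treatment assignments are assigned independently within Study 1501 and Study 1502". But if study explained 2-10% of residual variance in the primary ANCOVA, 90% power would become only 90.6-92.7%. The Study 2 SAP also plans results by original study for the primary analysis (Table 14.2.1.2c) and for this endpoint (Table 14.2.15.3).

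**Conclusion.** The concern holds as a matter of efficiency and consistency, not validity. The plans adjust comparable diary endpoints for baseline and give no reason for leaving this one unadjusted. The loss may be material and depends on rho, which is not stated: from 60-80% unadjusted power it runs from about 2 points at rho 0.2 to about 27 at rho 0.7. The simulated correlations of 0.45-0.84 point to the upper part of that range, but they follow from assumed seizure-rate distributions. The practical consequence lies mainly at Step 3.

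**What to change.** In Study 2 SAP section 8.2.1, before unblinding, make the Step 3 and Step 6 test a rank ANCOVA: ranks of longest interval as response, ranked baseline CSF as covariate, treatment and age group as factors. List age group explicitly, because the plan's descriptions of its rank ANCOVA do not name it. Make the matching edit to the key secondary endpoint list. Keep the Wilcoxon test and Hodges-Lehmann interval as supportive, and state that the adjusted p-value decides the step even if the unadjusted interval differs.

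The cost is SAP wording, since the data and the method are already in the plan. Study 1 was reported in September 2017, so there the adjusted analysis can only be supplementary.

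Adding study (1501/1502) as a factor is optional. It should not be required in the responder logistic model, where the Study 2 SAP already warns that the model may fail to converge.

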### 8.2.2. Additional Secondary Endpoint Analysis

#### **Number of Convulsive Seizure Free Days**

Convulsive seizure free days will be taken from the parent/caregiver diary data.

A convulsive seizure free day will be defined as a day for which diary data are available and no convulsive seizures have been reported. The total number of convulsive seizure free days will be summed for the entire T+M period and similarly for the baseline period.

Seizure free days per 28 days at baseline = (number of seizure free days during baseline)\*28/(number of days during baseline with non-missing diary data)

Seizure free days per 28 days during T+M Period = (number of seizure free days during T+M Period)\*28/(number of days during T+M Period with non-missing diary data)

Statistical comparison of treatment groups and placebo on the number of seizure free days per 28 days during T + M using the baseline as covariate will be done with a similar approach as the primary analysis.

#### **Responder Analyses: Proportion with ≥25 , 75% or 100% Reduction from Baseline in Convulsive Seizure Frequency**

A response curve will be generated for the mITT population. This graph will plot the % of subjects (y-axis) against percentage reduction in seizure frequency per 28 days in the T+M and M periods (x-axis). The horizontal axis will be the % reduction, and the vertical axis will be the % of subjects achieving ≥ that % reduction. In the graph, subjects experiencing an increase or no decrease in seizure frequency (i.e., ≤0 % reduction) will be regarded as having a 0% reduction in seizure frequency. Hence the ordinate for the 0 time point may not necessarily be at 100%. For example, if 15% of subjects have no reduction in seizure frequency during T+M period compared to the baseline period, the graph will start on the y-axis at 85%. The graph will be generated for all subjects, by treatment group.

This document is confidential.

## Statistical Analysis Plan

Sponsor: Zogenix International Limited; Protocol No.: ZX008 Study 2 (ZX008-1501 and ZX008-1502)

- The proportion achieving a  $\geq 25\%$  reduction from baseline in convulsive seizures will be analyzed for both treatment groups (ZX008 0.2 mg/kg/day and ZX008 0.8 mg/kg/day) comparing independently with placebo, using the same methods employed for the  $\geq 50\%$  reduction from baseline endpoint.
- The proportion achieving a  $\geq 75\%$  reduction from baseline in convulsive seizures will be analyzed for both treatment groups (ZX008 0.2 mg/kg/day and ZX008 0.8 mg/kg/day) comparing independently with placebo, using the same methods employed for the  $\geq 50\%$  reduction from baseline endpoint.
- The proportion achieving a 100% reduction from baseline in convulsive seizures, i.e., seizure-freedom, will be analyzed for both treatment groups (ZX008 0.2 mg/kg/day and ZX008 0.8 mg/kg/day) comparing independently with placebo, using the same methods employed for the  $\geq 50\%$  reduction from baseline endpoint.
- The proportion of subjects with near seizure freedom during the T+M period. Near seizure-freedom will be defined as having 0 or 1 seizures leading to a drop in the T+M period. These are additional secondary endpoints. Groups will be compared using the same methods employed for the  $\geq 50\%$  reduction from baseline endpoint.

A second response curve will be generated in which subjects who experience an increase in seizure frequency will be represented on the curve at horizontal axis at the position representing their increase in seizure frequency. Increases in seizure frequency will be represented to the left of the vertical axis on the figure.

